4.2. Variable Definitions

The following variables will only be calculated if not reported on the CRF.

4.2.1. Age

Participant age will be calculated as the integer part of the number of years from date of birth to the date of signing the informed consent form (ICF), using the following formula:

$$\text{Age} = \text{integer part of } (\text{date of informed consent} - \text{date of birth} + 1) / 365.25$$

4.2.2. Prior and Concomitant Medication

Prior medication is defined as any nonstudy medication started before the first dose of INCB050465.

Concomitant medication is defined as any nonstudy medication that is started accordingly:

- Before the date of first administration of INCB050465 and is ongoing throughout the study or ends on/after the date of first study drug administration.
- On/after the date of first administration of INCB050465 and is ongoing or ends during the course of study drug.

A prior medication could also be classified as "both prior and concomitant medication" if the end date is on or after first dose of INCB050465. In the listing, it will be indicated whether a medication is prior-only, concomitant-only, or both prior and concomitant medication.

For the purposes of analysis, all medications will be considered concomitant medications unless the medications can unequivocally be defined as not concomitant.

All participants receiving combination study treatment with INCB050465 and ruxolitinib are required to receive a standard PCP prophylaxis regimen determined by the investigator. A summary will be provided for PCP prophylaxis regimen.

4.2.3. Prior Ruxolitinib

A complete history of ruxolitinib usage before screening will be recorded on the CRF and produced as a listing by participant.

5. STATISTICAL METHODOLOGY

5.1. General Methodology

Unless otherwise noted, SAS® software (SAS Institute Inc, Cary, NC; v9 or later) will be used for the generation of all tables, graphs, and statistical analyses. Descriptive summaries for continuous variables will include, but not be limited to, the number of observations, mean, standard deviation, median, minimum, and maximum. Descriptive summaries for categorical variables will include the number and percentage of participants in each category.

5.2. Treatment Groups

As the study was terminated early, participants from all parts will be combined. Data will be summarized overall and by treatment group based on the dose regimen initially assigned in the initial portion:

- TG10: Ruxolitinib at stable dose plus INCB050465 10 mg QD for 8 weeks followed by 10 mg once weekly.
- TG20: Ruxolitinib at stable dose plus INCB050465 20 mg QD for 8 weeks followed by 20 mg once weekly.
- TG5, TG5I/M: Ruxolitinib at stable dose plus INCB050465 20 mg QD for 8 weeks followed by 5 mg QD.
- TG5D: Ruxolitinib at stable dose plus INCB050465 5 mg QD from Day 1 until EOT visit.

Note that TG5I/M in Part 4 is identical to TG5 from Part 3; participants from these 2 groups will be combined in the final analysis.

The crossover participants will be summarized in the initial portion from the date of randomization to the date before crossover.

In the crossover portion, the crossover participants will be summarized in TG5D from the date of crossover to the end of study. Only the crossover participants will be summarized in the crossover portion. Participants in TG5 (TG5I/M) and TG5D and the participants in TG10 or TG20 who do not meet the crossover criteria will remain in the treatment group initially assigned in the initial portion.

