### **5.2.3. Crossover of Part 2 or Part 3 Subjects**

It is anticipated that approximately 15 to 20 subjects will have been enrolled into Part 2. With IRB approval of Protocol Amendment 5 at a given site, subjects randomized to TG10 at that site may cross over to either 20 mg QD followed by 5 mg QD after Week 8 (if subject is within the first 8 weeks of treatment at the time of crossover), or to 5 mg QD (if subject is beyond 8 weeks of treatment and receiving 10 mg once weekly at the time of crossover). With IRB approval of Protocol Amendment 6 at a given site, subjects randomized to TG20 at that site may cross over to 5 mg QD once Week 8 has been reached. All potential crossover subjects must meet all of the following criteria:

1. Spleen size by palpation at most recent visit has decreased by < 25% from baseline while on study.
2. Has recent history of adequate bone marrow reserve as demonstrated by the following:
  - a. Platelet count  $\geq 50 \times 10^9/L$  in the 4 weeks before crossover.
  - b. ANC levels  $\geq 0.5 \times 10^9/L$  in the 4 weeks before crossover.
3. Has adequate liver function at most recent study visit as demonstrated by the following:
  - a. Direct bilirubin  $< 2.0 \times$  the ULN. (NOTE: direct bilirubin will only be determined if total bilirubin is  $\geq 2.0 \times$  ULN).
  - b. ALT or AST  $< 2.5 \times$  ULN.
4. Has adequate renal function at most recent visit as demonstrated by creatinine clearance  $> 50 \text{ mL/min}$  measured or calculated by Cockcroft-Gault equation.
5. Subject has been at least 85% compliant with study drug administration per drug accountability assessments at visits to date.
6. Subject has not developed a cardiovascular or gastrointestinal condition since Day 1 that would have excluded him/her from study entry.

Subjects who do not meet these criteria, or subjects who do meet the criteria but do not wish to cross over, may continue on the originally assigned regimen, and may crossover at any time provided the criteria for crossover are met and crossover is determined by subject and investigator to represent the best option.

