3.5. Crossover Portion

With IRB approval of Protocol Amendment 5 at a given site, participants randomized to TG10 in Part 2 at that site may cross over to either 20 mg QD followed by 5 mg QD after Week 8 (if participant is within the first 8 weeks of treatment at the time of crossover), or to 5 mg QD (if participant is beyond 8 weeks of treatment and receiving 10 mg once weekly at the time of crossover). With IRB approval of Protocol Amendment 6 at a given site, participants randomized to TG20 at that site may cross over to 5 mg QD once Week 8 has been reached. All potential crossover participants must meet the criteria listed in Protocol Amendment 6, Section 5.2.3.

Participants who do not meet these criteria, or participants who do meet the criteria but do not wish to cross over, may continue on the originally assigned regimen, and may crossover at any time provided the criteria for crossover are met and crossover is determined by participant and investigator to represent the best option.

The crossover portion starts when the participants are assigned to and receive their first dose of a different treatment. The original portion of the study for crossover participants ends the day before crossover.

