4.1.6. Handling of Missing and Incomplete Data

In general, values for missing data will not be imputed unless methods for handling missing data are specified in this section or relevant sections.

Partial MF diagnosis date will be handled as follows:

- If only the day is missing, then the imputed day will be the first of the month.
- If both the month and day are missing, then the imputed day and month will be 01 JAN.
- No imputation will be done if the date is completely missing.

Missing or partial date of last dose will be handled as follows:

- If only the day is missing, then the imputed date of the last dose will be the earlier date of the first day of the month or the date that the participant discontinued treatment.
- Otherwise, the date that the participant discontinued treatment will be used as the date of the last dose.

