7.4.2. Total Symptom Score and Total Symptom Score – Fatigue

The difference between TG5D and TG5 (TG5I/M) in change and percentage change in TSS from baseline to Week 12 and baseline to Week 24 evaluated by the MFSAF v3.0 symptom diary and the MPN-SAF will be assessed separately using a van Elteren test to account for stratification by ECOG performance status. If the study fails to enroll a sufficient number of participants in a particular stratum, the difference in the 2 treatment groups for these endpoints will be assessed separately using a 2-sample Wilcoxon rank sum test with a normal approximation applied to the test statistic as a sensitivity analysis. The difference between TG5D and TG5 (TG5I/M) in change and percentage change in TSS – Fatigue from baseline to Week 12 and baseline to Week 24 evaluated by the MFSAF v3.0 will use the same rule as regular TSS.

The difference in TSS between daily dosing (TG5D + TG5I/M) and daily/weekly dosing (TG10 + TG20) will be assessed in the same way.

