2.1 Primary Efficacy			
2.1.1.1	Summary of Percent Change in Spleen Volume by Visit	Safety Initial Portion	
2.1.1.2	Summary of Percent Change in Spleen Volume by Visit	Safety Crossover Portion	
2.1.1.3	Summary of Percent Change in Spleen Volume by Visit – Daily vs Daily/Weekly	Safety Initial Portion	
2.1.2.1	Van Elteren Test of Percent Change in Spleen Volume for TG5 (TG5I/M) and TG5D	Safety Initial Portion	
2.1.2.2	Van Elteren Test of Percent Change in Spleen Volume for Daily and Daily/Weekly Dosing	Safety Initial Portion	

Table No.	Title	Population	Standard
2.1.3.1	Summary of Response Categories for Spleen Volume Reduction for TG5 (TG5I/M) and TG5D	Safety Initial Portion	
2.1.3.2	Summary of Response Categories for Spleen Volume Reduction for Daily and Daily/Weekly Dosing	Safety Initial Portion	

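### Cutting TG10/TG20 data at response-dependent crossover enriches the weekly-dosing by-visit summaries for responders, while the spleen rank tests, read literally, err the other way

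*SAP*

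**What the plan says.** SAP 5.2 pools all study parts by initially assigned regimen and splits the data into an initial and a crossover portion. On the split it says: "The crossover participants will be summarized in the initial portion from the date of randomization to the date before crossover". SAP 3.5 agrees: "The original portion of the study for crossover participants ends the day before crossover". Later data go only to crossover-portion tables. TG5D and TG5 (TG5I/M) have no crossover route and stay in the initial portion throughout.

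Protocol 5.2.3 sets the conditions for crossover. The first is response-based: "Spleen size by palpation at most recent visit has decreased by < 25% from baseline while on study". Marrow, liver, renal, compliance and comorbidity conditions are added, and "All potential crossover subjects must meet all of the following criteria". Crossover is optional: "participants who do meet the criteria but do not wish to cross over, may continue on the originally assigned regimen". TG10 may cross after site approval of Amendment 5. TG20 may cross from Week 8 after site approval of Amendment 6.

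Three different missing-data positions then apply.
- By-visit summaries, for example Table 2.1.1.3 ("Summary of Percent Change in Spleen Volume by Visit – Daily vs Daily/Weekly"), are initial-portion tables with no imputation rule of their own, so SAP 4.1.6 governs: "In general, values for missing data will not be imputed unless methods for handling missing data are specified in this section or relevant sections".
- For the Week 12 spleen van Elteren test, SAP 7.3.1 gives missing volumes the largest increase and the lowest rank. SAP 7.4.1 carries the method to Week 24, and both sections plan a daily versus daily/weekly test (Table 2.1.2.2).
- For the symptom tests, SAP 7.4.2 gives no ranking rule for missing scores and says only: "The difference in TSS between daily dosing (TG5D + TG5I/M) and daily/weekly dosing (TG10 + TG20) will be assessed in the same way". Protocol 9.4.1.2 applies the primary-endpoint approach to the same tests.

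**The concern.** Leaving the weekly-dosing columns depends on response. A participant with a palpable decrease of 25% or more cannot cross and stays in. One with a smaller decrease may leave. Nothing comparable happens on the daily side. At visits after crossover, the TG10/TG20 columns of Tables 2.1.1.1, 2.1.1.3, 2.2.1.3, 2.2.5.3 and similar tables describe those who remained, not everyone assigned to the regimen.

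The same cut-off feeds the rank tests, where a missing spleen volume is treated as the worst outcome. One report could then show weekly dosing too favourably in the by-visit table and too unfavourably in the accompanying test, with no statement that both come from the crossover rule. Week 24 spleen volume and symptom scores are secondary endpoints, so a reader choosing between schedules would look at exactly these tables.

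**Working it through.** **The plan's own figure.** SAP 3.7.2 states 90% power with 30 per group, an 11.4-point shift, SD 14.5 and two-sided alpha 0.10. For a Wilcoxon test under normality, n = 2 × (14.5 × (1.645 + 1.282) / 11.4)² × π/3 = 29.0 per group. Power at 30 is 90.8% by this approximation and 89.8% by simulation. The figure reproduces. It is used below only for its mean, SD and 11.4-point yardstick.

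**Bias in the unimputed summaries.** Inputs from SAP 3.7.2: Week 12 percentage change with mean −8.44 and SD 14.5, taken as normal. Assumption: percentage volume change stands in for palpation (correlation 1).
- Share meeting the spleen condition: p = P(change > −25) = Φ((25 − 8.44)/14.5) = Φ(1.142) = 0.873.
- Mean among them: −8.44 + 14.5 × φ(1.142)/0.873 = −8.44 + 14.5 × 0.2078/0.873 = −4.99.
- Let f be the share of the pooled weekly group open to crossover by a visit, and u the share of the eligible who cross (not in the documents; shown as a range). The share removed is r = f × u × 0.873, and the remaining mean is (−8.44 + 4.99r)/(1 − r).

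**How many are open to crossover by Week 24.** Part 1 enrolled 10 and Part 2 enrolled 20 (Protocol 4.3.1). Protocol 5.2.3 speaks of randomized Part 2 or Part 3 subjects, so the 10 from Part 1 do not appear to be covered. About 28 of those 30 had been treated by the end of March 2018 (Protocol 1.5.4 and 1.8.3). Amendment 6 is dated 11 October 2018, 195 days or 27.9 weeks after 30 March, so nearly all Part 1 and Part 2 TG20 participants were past Week 24 before TG20 crossover existed. About 10 Part 2 TG10 participants remain, plus Part 3 TG20. With about 5 enrolled in Part 3 at 3:2, that is about 2, giving f = 12/32 = 0.375. At the cap of 15 (Protocol 4.1.3), f = 25/45 = 0.556.

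| Open to crossover | u = 25% | u = 50% | u = 75% |
|---|---|---|---|
| 12 of 32: remaining mean | −8.75 | −9.12 | −9.56 |
| shift / 11.4 | 2.7% | 5.9% | 9.9% |
| 25 of 45: remaining mean | −8.92 | −9.55 | −10.41 |
| shift / 11.4 | 4.2% | 9.7% | 17.3% |
| All (f = 1): remaining mean | −9.40 | −11.11 | −14.99 |
| shift / 11.4 | 8% | 23% | 57% |

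In this model the shift is proportional to the correlation between palpation and volume. At 0.5 the last row halves to about 4%, 12% and 29%.

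**Direction in the rank test.** A simulation used 30 weekly and 30 daily participants, no true difference, and an unstratified Wilcoxon test at two-sided 0.10. Assumptions outside the documents: palpation change with mean −20% and SD 30, correlation 0.3 to 0.9 with volume, and all weekly participants open to crossover, of whom 14% to 42% crossed before the scan.
- Crossovers given the lowest rank: weekly found worse in 13% to 82% of runs and better in at most 1.5% (nominal 5% each way).
- Crossovers dropped: weekly found better in 6% to 49% of runs.
- Observed weekly mean with crossovers dropped: −8.9 to −15.2, against a true −8.44.

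In the 12-of-32 case above, the share removed is 0.375 × 0.873 × u, or 8% to 25%. That overlaps only the lower part of the simulated crossing range, so the upper rates should not be read as forecasts.

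**The case against.** The strongest reply is that the effect on the planned comparisons is small, and in the spleen tests it is in the opposite direction. Most of this stands.

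- **A reader might infer that weekly dosing will look too good throughout.** The documents do not support that. SAP 7.3.1 and 7.4.1 give missing spleen scans the lowest rank, which counts against weekly dosing. The symptom tests may follow the same rule through Protocol 9.4.1.2, and SAP 10.1 declares no change from the protocol's analyses.
- **A reader might infer that participants are removed on the primary outcome itself.** The condition is palpation; the primary measure is MRI or CT volume. The two are related but not the same.
- **A reader might infer that non-responders as a whole are lost.** Crossover is optional, and those who fail a safety or compliance condition stay.
- **A reader might take 57% of the design difference as the likely size.** That needs every TG10/TG20 participant to be open to crossover and 75% of those eligible to cross. The enrolment counts and amendment dates contradict it for visits up to Week 24. The 11.4 points were also set for TG5D versus TG5I/M, so they serve here only as a scale.

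The daily versus daily/weekly contrast is also exploratory, the study ended early, the number of observations is printed, and post-crossover results are tabulated separately. These points lower the weight of the concern. They do not remove the selection in the by-visit columns, and printing n alone does not show who left or why.

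**Conclusion.** The concern holds for the unimputed by-visit spleen and symptom summaries: after crossover, their TG10/TG20 columns are enriched for responders, with no counterpart on the daily side. In the Week 12 and Week 24 spleen van Elteren tests of daily versus daily/weekly dosing, the bias runs against weekly dosing if a scan cut off by crossover is treated as missing, which is the literal reading; the SAP does not address the case explicitly. For the symptom tests the direction depends on whether the primary-endpoint approach applies.

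The size is uncertain because crossover counts are not given. At 25% to 75% crossing, the summary bias up to Week 24 is roughly 3% to 10% of 11.4 points for the pooled weekly group, or 4% to 17% if Part 3 TG20 reached 15. These figures assume normality, the SAP's Week 12 mean and SD, and palpation perfectly correlated with volume; a weaker correlation shrinks them. Week 12 is least exposed. Later visits are more so, because crossover may occur at any time and Part 2 TG20 participants also became able to cross. The point is worth correcting but does not threaten the TG5D versus TG5I/M primary comparison.

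**What to change.** In SAP 5.2, 7.3.1, 7.4 and Appendix A:
- Add by-visit spleen and symptom summaries, and daily versus daily/weekly tests, by initially assigned group. Use every collected scan and score at the nominal visit counted from the first INCB050465 dose, including those after crossover, and do not give these observed values the lowest rank.
- Keep the until-crossover tables, labelled as on-regimen results. Do not carry values forward in them: the first post-baseline scan is at Week 12, so anyone crossing before it would be assigned a 0% change.
- Print the number already crossed over at each visit.
- State in 7.3.1 and 7.4 how each test treats a value after crossover, and which missing-data rule the symptom tests use.

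The cost is SAP wording and reruns of existing tables. No new data are needed: visits are timed from Day 1, scans run every 12 weeks through Week 108 and the diary runs to Week 24. The downside is that post-crossover values include time on the crossover regimen, which dilutes the schedule contrast. That is why the two sets of tables should stand side by side.

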5.3. Analysis Populations

5.3.1. Safety Population

The safety population includes all participants in Parts 1, 2, 3, and 4 who received at least 1 dose of study drug. Treatment groups for this population will be determined according to the actual treatment the participant received regardless of assigned study drug treatment. The safety population will be used for all analyses.

The participants in TG5D and TG5 (TG5I/M) will be summarized under TG5D and TG5 (TG5I/M), respectively, in the initial portion. The participants crossed over from TG10/TG20 to TG5D will be summarized under TG10/TG20 in the initial portion before crossover and under a separate crossover group after crossover.

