#### **5.3.2.2. Supply, Packaging, and Labeling**

Subjects will continue to take the commercial supplies of ruxolitinib that have been prescribed for them.

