4. DATA HANDLING DEFINITIONS AND CONVENTIONS

4.1. Scheduled Study Evaluations and Study Periods

4.1.1. Day 1

Day 1 is the date that the first dose of study drug INCB050465 is administered to the participants. For randomized participants not treated with any study drug, Day 1 is defined as the day of randomization.

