4.1.4. Baseline Value

Baseline is the last nonmissing measurement obtained within the baseline window before the first administration of INCB050465, unless otherwise defined.

For randomized participants not treated with any study drug, baseline is defined as the last nonmissing assessment before randomization for all parameters.

When scheduled assessments and unscheduled assessments occur on the same day and time of the assessment or time of first dose is not available, use the following convention to determine baseline:

- If both a scheduled and an unscheduled visit are available on the day of the first dose and the time is missing, use the scheduled assessment as baseline.
- If all scheduled assessments are missing on the day of the first dose and an unscheduled assessment is available, use the unscheduled assessment as baseline.

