5.3.2. Spleen Volume Evaluable Population at Week XX

The spleen volume evaluable population includes all participants enrolled in the study who received at least 1 dose of study drug (INCB050465 or ruxolitinib), completed a spleen volume baseline assessment, and met at least 1 of the following criteria:

- The participant has Week XX spleen volume assessment.
- The participant has been on study for a minimum of $(7 \times XX + 7)$ days of follow-up.
- The participant has discontinued from treatment on or before Week XX.

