6.1. Baseline and Demographics, Physical Characteristics, and Disease History

Data will be summarized overall and by treatment group based on the dose regimen initially assigned for the safety population.

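### SAP 5.3.1 groups the population used for the primary test by treatment received; SAP 5.2, SAP 6.1 and the Protocol group by assignment, and SAP 10.1 declares no change

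*SAP*

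**What the plan says.** **Grouping in the SAP.** SAP 5.3.1 sets treatment groups in the safety population: they are "determined according to the actual treatment the participant received regardless of assigned study drug treatment. The safety population will be used for all analyses". Its second paragraph adds: "The participants in TG5D and TG5 (TG5I/M) will be summarized under TG5D and TG5 (TG5I/M), respectively, in the initial portion". SAP 5.2 has a different rule: "Data will be summarized overall and by treatment group based on the dose regimen initially assigned in the initial portion". The closing sentence of 5.2, in a paragraph on crossover, likewise leaves TG5 (TG5I/M) and TG5D participants in the group first assigned. SAP 6.1 applies the assigned rule to the same population: "Data will be summarized overall and by treatment group based on the dose regimen initially assigned for the safety population". SAP 7.3.1, which describes the primary analysis, names neither a population nor a grouping rule. Appendix A lists the primary van Elteren test (Table 2.1.2.1) under the safety population, initial portion.

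**The Protocol.** Section 9.4.1.1 restricts the primary comparison to subjects randomised to TG5D and to TG5I/M + TG5, without naming a population. Sections 9.4.1.2 and 9.4.1.3 name the ITT population for secondary and other efficacy analyses, and 9.1 defines it as everyone randomised.

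**The change record.** SAP 10.2.3 reports that ITT was removed and that the safety population now serves every analysis. It does not mention grouping by treatment received. SAP 10.1, the section for changes to Protocol-defined analyses, is marked as not applicable.

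**Study drug.** SAP 4.1.1 ties the term to INCB050465: "Day 1 is the date that the first dose of study drug INCB050465 is administered to the participants". SAP 5.3.2 includes either agent: "received at least 1 dose of study drug (INCB050465 or ruxolitinib), completed a spleen volume baseline assessment". In 5.3.1 it carries no qualifier.

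**The concern.** A programmer following the SAP can build the primary comparison in two ways. The two agree for anyone who started the assigned regimen. They can differ for two kinds of participant.

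1. **Started on a regimen other than the one assigned.** SAP 5.3.1 moves this participant to the other arm; SAP 5.2 does not.
2. **Randomised but never given INCB050465.** If *study drug* in 5.3.1 means INCB050465, this participant is excluded. If it means either agent, the participant is probably included, because everyone enters on ruxolitinib and "Subjects will continue to take the commercial supplies of ruxolitinib that have been prescribed for them". Grouping by treatment received then offers no group, while the missing-data rule in 7.3.1 would assign the worst rank in the stratum.

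The trial is open-label, and Protocol 6.1 allows up to 3 days between randomisation and the start of treatment. A participant could therefore learn the arm and decline, and such refusals need not be balanced between arms. Grouping by treatment received, or dropping the undosed, gives up the protection of randomisation for exactly these participants. Someone who consults only SAP 10.1 would not learn that the efficacy population and grouping differ from the Protocol.

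**Working it through.** **1. The plan's own power figure.** Inputs from SAP 3.7.2 and Protocol 9.2: 30 per group, shift 11.4, SD 14.5, two-sided alpha 0.10.

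- Standardised shift: 11.4 / 14.5 = 0.786.
- Wilcoxon efficiency under normality: 3/π = 0.955, so effective n = 30 × 0.955 = 28.65 per arm.
- Power = Φ(0.786 × √(28.65/2) − 1.645) = Φ(1.331) = 90.8%.
- Simulating the rank-sum test (40,000 runs) gives 90.1% power and 10.2% size.

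The stated 90% reproduces. The dispute concerns the text, not the sample size.

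**2. The passages side by side.**

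| Place | Who is analysed | Grouped by |
|---|---|---|
| Protocol 9.4.1.1 (primary) | randomised to the two groups | randomisation |
| Protocol 9.4.1.2–9.4.1.3 | ITT, all randomised | not stated |
| SAP 5.2 | all parts combined | regimen initially assigned |
| SAP 6.1 | safety population | regimen initially assigned |
| SAP 5.3.1 + Table 2.1.2.1 | at least 1 dose of *study drug* | treatment received |

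SAP 4.1.4 still provides for the undosed: "For randomized participants not treated with any study drug, baseline is defined as the last nonmissing assessment before randomization for all parameters". Under the INCB050465-only meaning of *study drug*, no analysis in the safety population could use that rule.

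Treatment received is also undefined for some participants. TG5/TG5I/M and TG20 share the same first 8 weeks, so anyone who stops before Week 8 cannot be placed in one or the other by what was taken.

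**3. What the choice can do to the primary test.** The documents do not give the number affected, so counts are assumed. Model: normal outcomes, SD 14.5, shift 11.4 favouring TG5I/M, two ECOG strata (assumed 4 of 30, or 2 of 15, per arm with ECOG 2), and 8,000 runs (standard error about 0.3 to 0.6 points). The 15-per-arm size is also an assumption, made because SAP 10.2.3 says enrolment ended early.

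Test: T = Σ W_h/(N_h+1), where W_h is the rank sum of one arm (n_h participants) in stratum h and N_h is the stratum total. Its null mean is Σ n_h/2, and its variance is tie-corrected. Reject when |Z| > 1.645.

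Rejection rate, never-dosed worst-ranked / dropped:

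| Case | 30 per arm | 15 per arm |
|---|---|---|
| None affected | 89.4% | 65.2% |
| 1, arm at random | 87.7 / 88.9% | 59.3 / 63.5% |
| 2, arms at random | 84.9 / 88.3% | 53.8 / 61.7% |
| 2, one in each arm | 87.1 / 89.0% | 53.7 / 61.6% |
| 2, both TG5I/M | 73.6 / 88.8% | 24.9 / 61.8% |
| 2, both TG5D | 94.3 / 88.8% | 80.2 / 62.5% |
| 2 at random, plus 10% other missing Week 12 scans | 69.0 / 72.8% | 39.0 / 45.9% |
| No true shift, 2 at random | 10.0 / 10.2% | 10.0 / 10.5% |
| No true shift, both TG5I/M | 11.6 / 9.7% | 13.6 / 10.5% |

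A separate unstratified simulation agrees for two in TG5I/M at 30 per arm: 74.1% worst-ranked, 89.4% dropped.

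**4. Wrong regimen started.** With one participant per arm given the other regimen, as randomised / as treated: 85.8 / 90.1% at 30 per arm, and 54.0 / 64.4% at 15 per arm. This assumes that outcome follows the regimen taken, so the as-treated figure simply returns to about the no-error level.

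**The case against.** **The SAP leans towards assignment.** SAP 5.2 (first and last sentences) and SAP 6.1 point to assignment, and the second paragraph of 5.3.1 is compatible with it. One general sentence points to treatment received. That the primary test is grouped as treated is an inference from 5.3.1 plus Appendix A. This narrows the conflict but does not remove it. The closing sentence of 5.2 does not address a wrong-regimen start, the second paragraph of 5.3.1 does not say whether its labels mean assigned or received, and 5.3.1 expressly claims all analyses.

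**The change is disclosed.** SAP 10.2.3 does report the loss of ITT, and Protocol 9.4.1.1 names no ITT population for the primary test. Both points are fair. But 10.2.3 logs changes between SAP versions and does not mention grouping by treatment received. The ITT analyses in Protocol 9.4.1.2 and 9.4.1.3 have been replaced without an entry in 10.1.

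***Study drug* may be an umbrella term.** SAP 6.4 applies it to each agent with a qualifier, so 4.1.1 can be read as one qualified use. Also, no table in Appendix A uses the 5.3.2 population, so harmonising 5.3.2 alters no listed output. What stands is that 5.3.1 lacks a qualifier at the point where it decides who is counted.

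**The effect may be nil.** This stands. Dosing follows randomisation closely and the IWRS assigns both group and drug, so few such participants are expected. The largest differences need small arms and both participants in the same arm. The wrong-regimen illustration shows dilution, not bias.

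**Conclusion.** The concern holds. The SAP gives two grouping rules for one population, does not say whether never-dosed randomised participants are counted, and declares no departure from the Protocol in the section meant for it.

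If nobody was affected, the results are identical under every reading. On the assumptions above, one never-dosed participant allocated at random moves power by about 1 point at 30 per arm (88.9 − 87.7 = 1.2) and about 4 points at 15 per arm (63.5 − 59.3 = 4.2). Two move it by 3.4 and 7.9 points. If both fall in TG5I/M, the gaps are 15.2 and 36.9 points. With no true shift and random allocation, both handlings stay near 10%. With both in one arm, worst-ranking gives 12 to 14%.

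No bias is shown to have occurred, and the average effect is small at the planned size. The rule should still be corrected, because the population and grouping of the primary test ought not to depend on which SAP section a programmer follows.

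**What to change.** - **TG5D versus TG5 (TG5I/M) efficacy tests:** include everyone randomised to these groups in Parts 3 and 4, by randomised group, with the existing worst-rank rule. Report the safety population as a sensitivity analysis.
- **Daily versus daily/weekly tests:** group by the regimen initially assigned. The SAP safety population includes Part 1, which was not randomised, so randomised group is unavailable for some of these participants.
- **SAP 5.3.1:** limit actual-treatment grouping to safety tables, and use assignment as the tie-breaker where regimens share the first 8 weeks. Make the section agree with 5.2 and 6.1.
- ***Study drug*:** use one stated meaning in 5.3.1 and 5.3.2.
- **SAP 10.1:** record the change of efficacy population from the Protocol.

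The cost is SAP wording and one population flag. Randomised assignment is already held in the IWRS, and no new data are needed. The sensitivity analysis and the tie-breaker go beyond the minimum repair, which is to confine the as-treated sentence to safety tables, qualify *study drug* and complete 10.1.
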